9.2 Endpoints

9.2.1 Safety Endpoints

- Adverse events (including explanations, revision surgery)
 - AEs,
 - ADEs,
 - SAEs,
 - SADEs and
 - AESIs.
- Device deficiencies
- Use of concomitant medication
- Compare baseline audiogram before implantation with audiogram at follow up visits to investigate if the thresholds have been constant over time. Bone- and air conduction thresholds, masked and unmasked, at 12 and 24 months.
- Socio-economic health care data will be collected at 12- and 24 months. It will be estimated and used at a later stage together with data from other sources.
 - Demographics: marital status, cohabitation, usual place of residence, education level
 - Employment status
 - Healthcare utilisation

- Hearing rehabilitation

9.2.2 Performance Endpoints

- The hearing performance at 12- and 24-months post-surgery when using the Investigational device compared to the hearing performance at of 3- and 6-months in the CBAS5751 investigation assessed as:
 - The change in Thresholds audiometry, sound-field [PTA4, mean of 0.5, 1, 2 and 4 kHz]
 - The change in Thresholds audiometry, sound-field [0.25, 0.5, 0.75, 1.0, 1.5, 2.0, 3.0, 4.0, 6.0 and 8.0 kHz].
 - The change in Adaptive speech in noise [signal-to-noise ratio, 50% speech understanding].
- BC Direct [0.25, 0.5, 0.75, 1.0, 1.5, 2.0, 3.0, 4.0 and 6.0 kHz] will be performed using the Investigational device at 12- and 24-months post-surgery.

9.2.3 Patient Reported Endpoints

- The benefit in self-reported hearing outcome when using the Investigational device at 12- and 24-months post-surgery compared with the benefit at 3- and 6-months post-surgery in the CBAS5751 investigation assessed by:
 - The change in scores using the Abbreviated Profile of Hearing Aid Benefit (APHAB).
 - The change in scores using the Speech, Spatial and Qualities of Hearing Scale (SSQ).
- The benefit in health-related quality of life (HRQoL) when using the Investigational device at 12- and 24-months post-surgery compared with the benefit at 3- and 6-months post-surgery in the CBAS5751 investigation.
- Usage information at 12 and 24 months:
 - Magnet choice
 - Sound Processor retention
 - Sound Processor wearing comfort
 - Use of SoftWear pad
 - Daily use
 - Daily streaming
 - Battery lifetime
 - Retention
 - Comfort
- Subjective questions at 12 and 24 months:
 - Every-day situation
 - Self-esteem
 - Sound quality

- Easy to use
- Durability
- Overall satisfaction (Yes/No)

9.2.4 Exploratory Endpoint

- High frequency thresholds [6.0, 7.0, 8.0, 9.0 and 9.5 kHz] will be collected with the CDI tool, using the Investigational device at 12- and 24-months post-surgery.

9.3 Hypotheses

No hypothesis testing will be made in the study. Confidence limits and p-values presented in the analyses are considered to be exploratory.

9.4 Sample Size Determination

This is a long term follow up study of the CBAS5751 study and no specific sample size calculation will be made here.

9.5 Analysis Populations

Subjects attending the 3- and/or the 6-months visit in the original CBAS5751 study who accept to participate in this long term follow up *investigation* and attends the 12- or 24 months visit will be analysed. No per protocol population will be defined.

9.6 Safety Endpoint Analyses

Separate tabulations of AEs, ADEs, SAEs, SADEs and AESIs will be produced. AEs, ADEs and AESIs will also be produced by severity (mild, moderate or severe) and relationship (related defined as Possibly, Probably and Definitely related). Number of events, number of subjects and percent of subjects with events will be presented by System Organ Class (SOC) and term in the CTCAE or IMDRF. Which system to be used will be decided and documented before the database is locked

Device deficiency will be summarized and presented as number and percentage. Device deficiencies will be presented totally and by relationship (Sound Processor, Implant, OFS or Accessories).

Concomitant medications will be presented in patient individual listings.

Descriptives for the socio-economic data, demographics and information on service utilisation related to hearing rehabilitation will be summarized for all patients.

9.7 Performance Endpoint Analyses

All performance variables will be presented by visit and changes where applicable according to paragraph 9.1. Wilcoxon signed rank test will be performed for changes in continuous variables over time, for changes in dichotomous outcomes Sign test will be used to evaluate better/equal/worse.

Analyses of PTA-4 thresholds and SNR vs overall satisfaction at 24 months will be made in order to find if there is any cut off point on these variables which predicts if a patient is satisfied or not. This will be made using logistic regression and c, ROC-curve and effect plot of predicted probability by PTA-4 and SNR will be presented.

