7 DESIGN OF THE CLINICAL INVESTIGATION

7.1 General

This is a multicentre, open, long term clinical investigation evaluating safety, performance and Patient Reported Outcomes (PRO) with the Osia 2 System in adult subjects 18 years or older with conductive hearing loss, mixed hearing loss or single-sided sensorineural deafness.

The subjects are the participants who performed the 3- and/or 6-month visit in the completed CBAS5751 investigation. The maximum number of subjects will be 27 from three clinics. The subjects will be followed at two visits, 12 and 24 months after the surgery date in the CBAS5751 investigation. The visit window at the 12-month visit will be opened as much as ± 5 months. The reason for this is to enable for as many subjects as possible to be included. At the time of investigation start the seven first implanted subjects in the CBAS5751 investigation have already passed their 12-month timepoint by several months. The performance of the device is not expected to change over this time period, but if it does, it will still be captured. This approach also provides the opportunity to collect safety data from the first seven subjects. At the final and most important time point 24 months, the visit window will be narrowed to ± 4 weeks.

The subjects will attend two scheduled investigation visits over a 12-month investigation period to be assessed as described in the Schedule of Events (Section 3). At investigation visits, subjects will be evaluated through objective audiological hearing tests, patient reported outcomes, questionnaires and safety assessments. The overall outcomes are to determine the hearing performance of the Investigational device at 12 and 24 months post-surgery and compare it with the last performed measurement (3 or 6 months) in the clinical investigation CBAS5751, assessed by sound-field thresholds audiometry, [PTA4, Mean of 0.5, 1, 2 and 4 kHz] and individual frequencies [0.25, 0.5, 0.75, 1.0, 1.5, 2.0, 3.0, 4.0, 6.0 and 8.0 kHz] and Adaptive speech recognition in noise. The self-reported outcomes will also be followed-up and compared with previous reported values. Safety will be assessed by recording and summarising all AEs/ADEs and DDs. A compilation of all AEs and DDs will be performed after all subjects have completed their 12-months visit. A full clinical investigation report will be prepared after the 24-month statistical analysis has been performed.

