7.3.2.2.4 Questions regarding the satisfaction with the device

At 12 and 24 months the subjects shall estimate the experience of the SP in relation to every-day situation, self-esteem, the easiness to use, durability of the device and sound quality using a Likert scale. It is a five- or seven-point scale which allows the individual to express how much they agree or disagree with a particular statement. The subjects shall also state if they are overall satisfied with the device, by answering yes or no.

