9 STATISTICAL CONSIDERATIONS

9.1 General Considerations

The distribution of continuous variables as well as change in continuous variables will be given as n, mean, SD, SEM, Median, Min and Max and the distribution of dichotomous and categorical variables will be given as number and percentages. Mean changes over time will be presented along with 95% CI.

All data will be presented in summarized tables and figures along with listings of individual data. The last non-missing measurement from the CBAS5751 investigation (3- and 6-months visits) will serve as the baseline reference in this follow up analysis for each subject. Changes from this baseline measurement will be evaluated statistically using a paired statistical methodology, each subject serves as his/her own control. Data collected at 12 and 24 months will be presented by visit where applicable. Data which are of collected continuously over time such as Adverse event and Device deficiency will be presented as Number of events and Number of subjects with events, and not by visits. Efficacy audiology measurements will be compared to the subjectively evaluation of the satisfaction with the system in order to find out if there are any useful clinical audiological cut-offs where a subject is satisfied or not.

Analyses at 12 months will be based on subjects attending the 12 months visit and analyses at 24 months analyses will be based on subjects attending the 24 months visit. No per protocol analyses will be performed and no imputation of missing data will be made.

Pass/fail criteria to be applied to the results:

- The objective is considered as fail if more than two of the subjects have experienced a related serious adverse event with the same root cause within the first 24 months from surgery.
- The objective is considered as fail if more than two of the subjects have an increase in PTA-4 Sound field threshold >15 dB at 24 months compared to the last obtained aided PTA value in CBAS5751 (3 or 6 months).
- The objective is considered as fail if more than two of the subjects have an increase in SNR field threshold >1 unit at 24 months compared to the last obtained aided SNR value in CBAS5751 (3 or 6 months).

If a failed result regarding PTA-4 or SNR is obtained a root cause analysis will be performed to confirm that the failed value depends on declined performance and not on other factors such as impaired unaided hearing, incorrectly performed tests or other causes.

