If any of the criteria are failed the investigation is considered as fail.

No formal hypothesis testing will be performed in this long term follow up study.

No termination of the study will be made on statistical grounds.

Protocol deviations will be listed in listing appendix.

No Statistical Analysis Plan (SAP) is planned to be produced.

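### Section 9.7 reads c and any satisfaction cut-off from the same subjects (at most 27) that produced them, with no interval or optimism correction named: a minor weakness of an exploratory analysis

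*Combined protocol and SAP*

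**What the plan says.** The outcome is one binary item from the satisfaction questionnaire (section 7.3.2.2.4): "The subjects shall also state if they are overall satisfied with the device, by answering yes or no". Section 9.7 relates it to PTA-4 and SNR at 24 months "in order to find if there is any cut off point on these variables which predicts if a patient is satisfied or not", and gives the method as "This will be made using logistic regression and c, ROC-curve and effect plot of predicted probability by PTA-4 and SNR will be presented". Section 9.1 states the purpose as to "find out if there are any useful clinical audiological cut-offs where a subject is satisfied or not".

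On numbers, section 7.1 says "The maximum number of subjects will be 27 from three clinics", and section 9.4 says "no specific sample size calculation will be made here". Withdrawn subjects are not replaced (section 7.2.6). The 24-month analyses use those who attend that visit, without imputation (section 9.1), so 27 is an upper limit.

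The plan names no rule for choosing the cut-off, no confidence interval for c or for the cut-off, and no internal validation. Section 9.1 promises 95% intervals for mean changes over time only. It also says "No Statistical Analysis Plan (SAP) is planned to be produced", so no later statistical document is planned to supply the detail.

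**The concern.** A c statistic and a best cut-off that are chosen and judged in the same small sample look better than they are. The information in a yes/no outcome is set by the smaller group. If few subjects are dissatisfied, the ROC curve rests on those few, and a threshold placed where it separates them best will look informative even when hearing performance has nothing to do with satisfaction.

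At stake is how the result is read. The plan wants cut-offs that are useful in the clinic. Given only a c, a curve and a threshold, a reader has no means of telling a real relation from chance.

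**Working it through.** The plan gives no expected c, satisfaction rate or power, so it has no figure of its own to reproduce. The check asks what the stated method returns when PTA-4 and SNR are unrelated to satisfaction.

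**Inputs.** N = 27 (section 7.1, the maximum). The number dissatisfied, m, is not in the documents. It is an assumption, taken from 2 to 8, with n = 27 − m satisfied.

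**1. What m might be.** At assumed dissatisfaction rates of 5%, 10%, 15%, 20% and 30%, the expected m is 27 × rate = 1.4, 2.7, 4.1, 5.4 and 8.1. The binomial chance of 5 or fewer dissatisfied is 0.998, 0.95, 0.79, 0.54 and 0.14. The chance of 0 or 1, when hardly any model can be fitted, is 0.61, 0.23, 0.07, 0.02 and 0.001.

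**2. One predictor, direction chosen by the fit.** With no association, c has mean 0.50 and SE = √[(N + 1)/(12·m·n)].
- m = 2: √[28/(12 × 2 × 25)] = 0.216
- m = 4: √[28/(12 × 4 × 23)] = 0.159
- m = 8: √[28/(12 × 8 × 19)] = 0.124

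If the fitted sign decides the direction, c cannot fall below 0.50, and its mean is about 0.50 + SE·√(2/π). That gives 0.67, 0.63 and 0.60. The exact rank distribution gives 0.68, 0.63 and 0.60.

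**3. One predictor, direction fixed beforehand** (worse PTA-4 or SNR means less satisfied). Mean c is 0.50, so c is unbiased. The chance of c ≥ 0.70 comes from the exact rank distribution. For m = 2, 72 of the 27 × 26/2 = 351 equally likely rankings qualify, and 72/351 = 20.5% (simulation gave about 22%). For m = 4 and m = 8 it is 10.8% and 5.3%. The value 0.70 is only a yardstick; the plan sets no threshold.

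**4. Best cut-off, direction fixed.** Sensitivity plus specificity at the best threshold was averaged over 40,000 random rankings for each m. A predictor with no information has a true value of 1.

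**5. Both predictors fitted jointly.** Null simulation of a two-predictor logistic model.

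| m of 27 | Mean c, fitted direction | P(c ≥ 0.70), fixed direction | Sens + spec at best cut-off, fixed direction | Mean c, joint model |
|---|---|---|---|---|
| 2 | 0.68 | 20.5% | 1.38 | 0.76 |
| 4 | 0.63 | 10.8% | 1.29 | 0.70 |
| 8 | 0.60 | 5.3% | 1.23 | 0.65 |

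**6. Precision when there is a real relation.** Hanley–McNeil SE at a true c of 0.80, with Q1 = 0.8/1.2 = 0.667 and Q2 = 1.28/1.8 = 0.711. For m = 4: √[(0.16 + 3 × 0.0267 + 22 × 0.0711)/92] = 0.14, so an approximate 95% half-width is 1.96 × 0.14 = 0.27. For m = 8 the SE is 0.10. An interval would make this imprecision visible.

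**The case against.** The strongest reply is that alarming rates come from counting results that nobody would believe. With 4 dissatisfied and no association, a joint model reaches c ≥ 0.70 in about 47% of simulated studies. A reader might infer that the plan would hand the sponsor a convincing cut-off about half the time. The documents do not support that. Many of those fits have better hearing predicting dissatisfaction, and the effect plot that section 9.7 already requires would show it. With both signs as expected, the joint figure is about 12%. For one predictor in the expected direction it is about 11%, and c is not biased at all. Section 9.7 also does not state a joint model; separate models are a natural reading, because a cut-off on each variable comes from its own ROC curve.

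The number dissatisfied has no source in the documents, so few dissatisfied is an assumption, and the effect shrinks as m grows.

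The analysis also has low standing. It is not among the objectives or endpoints (sections 6 and 9.2) or the pass/fail criteria (section 9.1). Section 9.3 calls confidence limits and p-values exploratory. The wording leaves room for finding no cut-off, and individual data will be listed. Section 4.1 mentions marketing claims, but it ties none of them to a cut-off.

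All of this stands, and it limits the point. It does not remove it. The exploratory label covers confidence limits and p-values, whereas the outputs here are c and a threshold with no interval named. The best cut-off stays optimistic even when the direction is fixed.

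**Conclusion.** The point holds as a minor improvement to an exploratory analysis. With 2 to 8 of 27 dissatisfied (assumed) and no association, apparent c averages about 0.68 to 0.60 for one predictor if the fit sets the direction, and 0.76 to 0.65 for a joint model if one is used. Fixing the direction removes the bias in one-predictor c. It leaves a chance of about 21% to 5% of reaching 0.70, and a best cut-off whose sensitivity plus specificity exceeds its true value by about 0.38 to 0.23. These sizes rest on the assumed m and on all 27 subjects attending at 24 months.

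A reader might go further and conclude that the analysis should move to the Likert items, or that it needs a fixed minimum number of dissatisfied subjects, a penalised fit, or a rule that suppresses the cut-off when the interval for c includes 0.5. The documents do not support these as corrections. Section 7.3.2.2.4 lists no graded item for overall satisfaction, so the Likert items would change the question and could not give the cut-off sought. The other three are preferences. Nothing here touches the study's pass/fail result.

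**What to change.** Amend section 9.7 as follows.

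- Fit PTA-4 and SNR in separate models, and state now that worse values are expected to go with dissatisfaction. Compute c in that direction, so that it can fall below 0.50.
- Report c with a 95% confidence interval and a bootstrap optimism-corrected value. With one predictor and a fixed direction the interval does most of the work. The correction matters more if the direction is fitted or the predictors are combined: in a null simulation of the joint model it lowered mean c from 0.71 to 0.59, more than half of the excess over 0.50 (0.12 of 0.21).
- Report any cut-off with its bootstrap interval and with optimism-corrected sensitivity and specificity, next to the number of dissatisfied subjects.
- Label any cut-off hypothesis-generating.

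The cost is a few lines of text and a little more programming, with no new data or visits. The bootstrap results will themselves be imprecise if very few subjects are dissatisfied. The sponsor may end with a less favourable c, or with no usable cut-off.

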9.8 Patient Reported Outcomes Endpoint Analyses

All patient recorded variables will be presented by visit and changes where applicable according to paragraph 9.1. Wilcoxon signed rank test will be performed for changes in continuous variables over time, for changes in dichotomous outcomes Sign test will be used to evaluate better/equal/worse.

9.9 Exploratory Endpoint Analyses

High frequency thresholds [at 6.0, 7.0, 8.0, 9.0 and 9.5 kHz] will be presented by visit, both individual and mean values.

9.10 Interim Analyses

An interim safety analysis will be performed when all subjects have completed their 12-months visit. A compilation of all AEs and DDs that occurred between the 6-months visit in CBAS5751 and the 12-months visit in this investigation will be performed. In addition, follow-up of any unresolved AEs at the 6-month visit in CBAS5751 will be done.

10 INFORMED CONSENT PROCESS

The Investigator shall obtain written informed consent from the subject using an approved ICF prior to any clinical investigation-related examination or activity. The rationale of the clinical investigation, as well as the risks and benefits, what participation will involve, and alternatives to participation will be explained to the subject. Ample time will be provided for the subject to enquire about details of the clinical investigation and to decide whether to participate.

All questions about the clinical investigation shall be answered to the satisfaction of the subject or the subject's legally acceptable representative. Subjects shall not be coerced or unduly influenced to participate or to continue to participate in a clinical investigation.

Each subject (or their legally authorised representative) and the person who conducted the informed consent discussion, shall sign and date the Informed Consent Form (ICF). Where required, a witness shall sign and personally date the ICF. A copy of the signed ICF shall be given to the subject. The original signed ICF shall be archived in the Investigator's Site File or subject file at the investigational site.

The subject, or the subject's legally authorised representative, shall be informed in a timely manner if new information becomes available that may be relevant to the subject's willingness to continue participation in the clinical investigation. The communication of this information must be documented as an update to the ICF and re-consent of the subject.

11 ADVERSE EVENTS AND DEVICE DEFICIENCIES

11.1 Definitions

11.1.1 Adverse Event

An adverse event (AE) is any untoward medical occurrence, unintended disease or injury, or untoward clinical signs (including abnormal laboratory findings) in subjects, users or other persons whether or not related to the medical device or the procedures required for implant or use.

NOTE 1: This definition includes events related to the medical device or the comparator device.

NOTE 2: This definition includes events related to the procedures involved.

NOTE 3: For users and other persons, this definition is restricted to events related to medical devices.

11.1.2 Adverse Device Effect

An adverse device effect (ADE) is an AE related to the use of a medical device.

NOTE 1: This includes any AE resulting from insufficiencies or inadequacies in the instructions for use, the deployment, the implantation, the installation, the operation, or any malfunction of the medical device.

NOTE 2: This definition includes any event resulting from use error or from intentional misuse of the medical device.

11.1.3 Serious Adverse Event

A serious adverse event (SAE) is any AE that:

- a) led to a death,
- b) led to a serious deterioration in the health of the subject that either resulted in:
 - a life-threatening illness or injury, or
 - a permanent impairment of, or damage to, a body structure or a body function, or
 - in-patient hospitalisation or prolonged hospitalisation, or
 - medical or surgical intervention to prevent life-threatening illness or injury or permanent impairment or damage to a body structure or a body function, or
 - Chronic disease.
- c) led to foetal distress, foetal death or a congenital physical or mental abnormality, or birth defect

NOTE: Planned hospitalisation for a pre-existing condition, or a procedure required by the CIP, without serious deterioration in health, is not considered a SAE.

11.1.4 Serious Adverse Device Effect

A serious adverse device effect (SADE) is an ADE that has resulted in any of the consequences characteristic of a SAE.

11.1.5 Unanticipated Serious Adverse Device Effect

An unanticipated serious adverse device effect (USADE) is a SADE, which by its nature, incidence, severity, or outcome has not been identified in the current version of the Investigator's Brochures (3) (4).

NOTE: An anticipated serious adverse device effect is an effect, which by its nature, incidence, severity, or outcome has been identified in the Investigator's Brochure.

